## LIST OF ABBREVIATIONS

Define all unusual or 'technical' terms related to the trial/study\*. Add or delete as appropriate. Maintain alphabetical order for ease of reference.

AE	Adverse Event
AR	Adverse Reaction
CI	Chief Investigator
CRF	Case Report Form
GCP	Good Clinical Practice
DOI	Digital Object Identifier
ICF	Informed Consent Form
DMC	Independent Data Monitoring Committee
ISF	Investigator Site File
ISRCTN	International Standard Randomised Controlled Trials Number
NIMP	Non-Investigational Medicinal Product
ORLAU	Orthotic Research & Locomotor Assessment Unit
PI	Principal Investigator
PIC	Participant Identification Centre
PIS	Participant Information Sheet
QA	Quality Assurance
QC	Quality Control
REC	Research Ethics Committee
RJAH	Robert Jones and Agnes Hunt
SAE	Serious Adverse Event
SAR	Serious Adverse Reaction
SDV	Source Data Verification
SMF*	Study Master File
SMG*	Study Management Group
SOP	Standard Operating Procedure
SSI	Site Specific Information
SUSAR	Suspected Unexpected Serious Adverse Reaction
TMG*	Trial Management Group
TSC	Trial Steering Committee
TMF*	Trial Master File

## STUDY SUMMARY

Trial/Study* Title	Shoulder instability in children: understanding muscle activity and movement pattern differences	
Internal Ref. Number (or short title)	Shoulder instability in children: muscle activity and movement v2.0	
Trial/Study* Design	Cohort observation Cross-sectional study	
Trial Intervention (where applicable)	N/A	
Trial/Study* Participants	15 children (aged between 8 and 18) with shoulder instability 15 age matched controls	
Planned Sample Size	30 participants	
Treatment duration	2 hours 30 minutes maximum	
Follow up duration	12 months	
Planned Trial Period	24 months	
	Objectives	Outcome Measures
Primary	*	
Secondary		

\* This is not an experimental study and so there is not a single/primary outcome measure. The following outcomes will be derived from this study

[figure not shown]
*For the single movement analysis session:*

- **Kinematic** variables related to the movement tasks, for example
  - joint angles (degrees)
  - displacement (position, speed and associated derivatives)
- **Kinetic** variables related to the movement tasks, for example
  - forces/ strength (n, kg/force)
- **Muscle activity patterns** related to the movement tasks, for example
  - Surface electromyography (sEMG) (mv)

*For the follow up outcomes:*

- Number of recurrent episodes of instability

## STUDY FLOWCHART

## 1 BACKGROUND

The aim of this study is to identify factors responsible for recurrent shoulder instability in children. Shoulder instability, i.e. complete or partial dislocation of the shoulder joint, is common in children, resulting in pain and disability. Recurrent instability can damage the shoulder joint resulting in the premature development of arthritis.

Rehabilitation approaches are preferred over surgical methods for the growing child e.g. physiotherapy to restore movement and prevent further instability. Existing rehabilitation procedures are based on addressing factors assumed to be responsible for instability e.g. physiotherapists may try to increase shoulder stability by building up the shoulder muscles to compensate for the damaged ligaments. It is evident however that we do not fully understand the mechanisms of shoulder instability as failure rates for physiotherapy are high, with 70% - 90% of children continuing to suffer recurrent instability. This is an observational, cross-sectional study of children (aged 8 to 18) presenting with shoulder instability of any origin, traumatic or atraumatic (n=15) and an age-matched sample (n=15) with no history of shoulder problems. Muscle activity and movement pattern differences will be measured using non-invasive 3D motion capture and surface electromyography, to identify factors responsible for instability. Only a single visit to the site will be required (The Orthotic Research & Locomotor Assessment Unit (ORLAU) based at The Robert Jones & Agnes Hunt Orthopaedic Hospital NHS Foundation Trust in Oswestry.).

If we better understand the mechanisms associated with instability, we can better target physiotherapy interventions to reduce dislocations and disability. If we identify specific patterns of activity associated with instability, these could be addressed through personalised and improved exercise prescription and rehabilitation. Additionally, we may identify causes of instability for which physiotherapy may not be appropriate, therefore ensuring patients are referred to the correct service in a timely manner, improving patient outcomes and allocating physiotherapy resources more appropriately. Participants will be recruited from musculoskeletal/orthopaedic outpatient clinics. This study is funded by the Private Physiotherapy Education Foundation.

## 2 RATIONALE

Mechanisms of shoulder instability, and the subsequent development of arthritis, are poorly understood (Deitch, Mehlman et al. 2003, McFarland, Kim et al. 2003, Barden, Balyk et al. 2005, Barrett 2015). Both surgical and nonsurgical interventions are based on a current understanding of the associated mechanisms that may include anatomical predisposition (shallow glenoid, lax ligament and capsule), weak muscles, or inappropriate muscle coordination (Harryman, Sidles et al. 1992, Cordasco 2000, Inui, Sugamoto et al. 2002, Deitch, Mehlman et al. 2003, McFarland, Kim et al. 2003, Barden, Balyk et al. 2005, Hovelius and Saeboe 2009, Jaggi and Lambert 2010, Jaggi, Noorani et al. 2012, Barrett 2015, Longo, van der Linde et al. 2016, Bateman, Jaiswal et al. 2018, Best and Tanaka 2018).

Rehabilitation approaches are preferred over surgical methods for the growing child, and management is therefore aimed at addressing predominant factors associated with these mechanisms e.g. exercises to improve co-ordination of the shoulder muscles if the source of instability is dysfunctional muscle control. However, failure rates are high (approximately 70% - 90%), indicating that current understanding of these mechanisms is limited.

In children, this can have detrimental long-term effects. This research is important as shoulder instability, mainly subluxation and dislocation, is common (23.9/100,000 person years but can be as high as 164.4 for 14 -16 year olds) (Leroux, Ogilvie-Harris et al. 2015) resulting in pain, decreased movement and functional limitations. Diagnosis of shoulder instability is normally delayed (on average by 2-years) and 70% of children have repeated dislocations (Longo, van der Linde et al. 2016), often associated with premature glenohumeral arthropathy (odds ratio 19.3) (Marx, McCarty et al. 2002, Deitch, Mehlman et al. 2003).

Shoulder stability results from complex mechanisms comprising finely balanced forces in ligaments, muscles and joint surfaces. These can be disrupted in a range of neuromuscular disorders and joint degradation, and are vulnerable to traumatic injury. Currently, we are unable to capture this complexity to quantify instability during dynamic upper limb tasks performed during clinical assessment and rehabilitation (Marchi, Blana et al. 2014). Biomechanical or mathematical modelling of this complex structure can help to understand the mechanisms associated with instability and predict outcomes for surgical and non-surgical interventions. Loading on internal structures that cannot be measured can also be estimated by this approach. Furthermore, approximately 30% of patients who have surgical stabilisation of their shoulder go on to sustain further episodes of instability (Deitch, Mehlman et al. 2003).

This project is therefore a fundamental step, in the development of biomechanical models which can ultimately be used to further our understanding of the shoulder, specifically behaviour of the articulating bony surfaces and muscle forces.

### 3 OBJECTIVES AND OUTCOME MEASURES/ENDPOINTS

#### 3.1 Primary objective

- The primary objective of this study is to identify factors responsible for recurrent shoulder instability in children.

In order to meet the main objective of this study, a series of secondary objectives need to be met.

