#### 3.2 Secondary Objectives

The secondary research objectives used to address the main aim of the study are:

- Validation of a 3D movement analysis protocol for measuring upper limb function in children with shoulder instability.
- Obtain new data on muscle activity and movement patterns of children with and without shoulder instability
- Categorising clinical presentations of instability and identification of important factors for recurrent instability

This is not an experimental study and so there is not a single/primary outcome measure. The following outcomes will be derived from this study

*For the single movement analysis session:*

- **Kinematic** variables related to the movement tasks, for example
  - joint angles (degrees)
  - displacement (position, speed and associated derivatives)
- **Kinetic** variables related to the movement tasks, for example
  - forces/ strength (n, kg/force)
- **Muscle activity patterns** related to the movement tasks, for example
  - Surface electromyography (sEMG) (mv)

*For the follow up outcomes:*

- Number of recurrent episodes of instability

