## 8 STATISTICS AND DATA ANALYSIS

### 8.1 Sample size calculation

This is an observational, cross-sectional study.

- A power calculation, used to determine the required sample size, is not possible for this study as the standard error of measurement (SEM - essential to identify a minimally clinically important difference) is not known.
- This study will provide the data from which SEM can be estimated and this can then be used to inform power calculations for future studies.
- Our rationale for selecting a sample size of 15 in each group (30 total) has been based on previous work which has developed and then implemented protocols for clinical practice.
- The two references cited below have developed clinical measurement protocols using sample sizes of 10 typically developing children and 12 children with cerebral palsy affecting the upper limbs.
- In the absence of an equivalent study in paediatric shoulder instability a sample size of 15/group reflects the current research practice in the literature and will be able to provide us with population estimates of “standard error of measurement - SEM” in typically developing children and those with upper limb pathology.

Jaspers, E., et al., Upper limb kinematics: development and reliability of a clinical protocol for children. *Gait Posture*, 2011. 33(2): p. 279-85.

Jaspers, E., et al., The reliability of upper limb kinematics in children with hemiplegic cerebral palsy. *Gait & Posture*, 2011. 33(4): p. 568-575.

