### **Measurement burden**

In order to minimise the measurement burden on all participants and ensure the aims of the study are met, our study design has been developed following input from a Public Involvement and Engagement

(PPIE) group, an additional 7 children of appropriate age groups outside of the PPIE and clinicians who routinely work with children with shoulder instability.

A primary aim of our study is to test the reliability and variability of a measurement analysis protocol in children with shoulder instability and age-matched controls. To minimize the measurement burden on children and their parent/carer/guardian, only a single study site visit, lasting a maximum of 2 hours 30 minutes, is required. Reliability will be determined by a sensitivity analysis in which we will virtually perturbate the markers post data collection. This has been selected to minimise the measurement burden of multiple visits for children with shoulder instability and the age matched controls. For children with shoulder instability this will also minimise the variability which may arise as a result of the natural recovery process over time and confound our results. The measurement protocol has been designed after consultation with different children of appropriate age groups, clinicians and the scientific literature.

Where possible, we will additionally try and accommodate measurement sessions outside of school hours for both groups to limit any school/lesson absences.

Diaries and monthly telephone calls (lasting up to 12 months), have been selected to ensure accurate recordings of the events and minimise recall bias. We have received input re the follow up study processes and diaries from the Public Involvement and Engagement group and additional children of appropriate age groups. We do not anticipate that participants will have a large number of instability episodes and so the measurement burden for recording will be minimal. Additionally, participants will only be asked to record when an episode happens.

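### The primary objective claims factors responsible for recurrence, but the sample size is argued only for measurement error, no planned analysis uses the follow-up episodes, and the order of aims is not reconciled

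*Combined protocol and SAP*

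**What the plan says.** The primary objective in section 3.1 reads: "The primary objective of this study is to identify factors responsible for recurrent shoulder instability in children". Sections 1 and 8.3 give the same aim. Section 3.1 then sets a stepwise order: "In order to meet the main objective of this study, a series of secondary objectives need to be met". The first of those secondary objectives, in sections 3.2 and 8.3, is: "Validation of a 3D movement analysis protocol for measuring upper limb function in children with shoulder instability".

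Section 11, under Measurement burden, ranks that item differently: "A primary aim of our study is to test the reliability and variability of a measurement analysis protocol". It goes on to use this aim in explaining the single visit.

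On outcomes, section 3.2 says: "This is not an experimental study and so there is not a single/primary outcome measure".

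On size, section 8.1 says a power calculation is not possible because the SEM is unknown. It supports 15 per group by two protocol-development studies, with 10 typically developing children and 12 children with cerebral palsy, and adds: "This study will provide the data from which SEM can be estimated". It says nothing about detecting or estimating a factor for recurrence.

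On recurrence, section 7.8 collects instability episodes by diary and monthly telephone call for up to 12 months. Section 8.3 describes the session measures, computes coefficients of variation and SEM, and perturbs the virtual markers. It then looks for groups by a clustering method to be chosen once the data are known, with a conditional ANOVA or t-test. The episode count appears in none of these analyses.

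**The concern.** A primary objective fixes what the final report may claim. Here it uses a causal word, responsible, and section 1 expects the findings to guide personalised exercise prescription and referral. The design does not back that claim in two respects. The sample size was argued for a different quantity: within-child measurement error rather than differences between children who do and do not recur. And the data that bear on recurrence are collected but have no planned analysis.

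The conflicting rank of the reliability aim adds to this, because a reader cannot tell from the documents which aim is the main one. At stake is a headline about factors for recurrence drawn from a study that was neither sized nor analysed to give it.

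**Working it through.** **1. The plan's own figure.** There is nothing to reproduce. Section 8.1 gives no alpha, power, effect size, SD or precision target, and precedents of 10 and 12 do not yield 15 by any stated rule. What follows is what 15 children deliver for each aim.

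**2. Recurrence aim.** Inputs from the documents: 15 cases (section 4); 70%-90% of children continuing to have recurrent instability (section 1, no time frame given). Assumptions: two-sided 5%; 80% power; the 70%-90% applies over 12 months; recurrence reduced to yes/no; one continuous feature.

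Expected number with recurrence: 15 × 0.70 = 10.5; 15 × 0.80 = 12; 15 × 0.90 = 13.5. Whole-number splits therefore run from 10/5 to 14/1.

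Method: two-sample t-test with n1 + n2 − 2 = 13 degrees of freedom, critical value 2.16, noncentrality d/√(1/n1 + 1/n2), power from the noncentral t. The 95% CI half-width in SD units is 2.16 × √(1/n1 + 1/n2). For 10/5 this is 2.16 × 0.548 = 1.18; for 14/1 it is 2.16 × 1.035 = 2.24.

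| Split | Detectable difference (SD) | Power at 0.8 SD | 95% CI half-width (SD) |
|---|---|---|---|
| 10/5 | 1.66 | 27% | 1.18 |
| 11/4 | 1.77 | 25% | 1.26 |
| 12/3 | 1.96 | 21% | 1.39 |
| 13/2 | 2.30 | 16% | 1.64 |
| 14/1 | 3.14 | 11% | 2.24 |
| 8/7 (most even) | 1.57 | 30% | 1.12 |

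At 90% recurrence the chance that no child is free of recurrence is 0.9^15 = 21%.

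The 15 v 15 contrast has a detectable difference of 1.06 SD and 56% power at 0.8 SD. It compares instability with no instability, so it does not answer the recurrence question.

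**3. Measurement-error aim.** Assume a within-session SEM from k repetitions per child, treated as independent. Then df = 15(k − 1), and the 95% limits are the estimate times √(df/χ²), taken at the 97.5% and 2.5% points. Section 7.7.2 allows at most 6 repetitions for loaded tasks and 12 for unloaded tasks.

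- k = 6: df = 75; √(75/100.8) = 0.86 and √(75/52.9) = 1.19.
- k = 12: df = 165; √(165/202.5) = 0.90 and √(165/131.3) = 1.12.

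This SEM mixes natural movement variation with measurement error. Because markers are placed once, it contains no re-placement error.

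**4. Analysis against data.** Section 8.3 has no step with recorded episodes on one side and a movement or muscle feature on the other. The conditional ANOVA or t-test compares groups found by clustering, not groups defined by recurrence.

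**The case against.** The strongest reply is that the governing sections agree with each other. Sections 3.1, 3.2 and 8.3 set out a hierarchy in which validation is a step towards the main aim, and section 11 uses the indefinite article in a paragraph about burden. That stands: this is one unreconciled phrase, and a reader who infers that section 11 asserts the opposite of section 3 goes too far. Correcting the phrase does not, however, give section 8.1 a rationale for the recurrence objective.

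A reader might also infer that the deciding result can be chosen afterwards. The documents do not support this. They name no primary outcome and no success rule, and section 8.3 is mainly descriptive, so there is no verdict to switch.

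Nor is the size limit hidden. Section 8.1 says power cannot be calculated and that the data will inform later studies, and section 8.3 makes its tests conditional on a large enough sample. This weakens any suggestion of concealment but leaves the wording of section 3.1 unsupported.

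The power figures rest on a contrast the plan does not specify. The 70%-90% has no time frame, the follow-up outcome is a count, and sections 6.1.1 and 7.4 would also allow recurrence to be classed at baseline. All of this stands, so the figures are illustrative. The 8/7 row caps any two-group split of the 15 at about 30% power for 0.8 SD.

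Finally, it is tempting to say that 15 children are shown to be enough for reliability. They are not. Sections 8.3 and 11 rely on virtual marker perturbation for reliability, and the limits in step 3 cover within-session repetition only.

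**Conclusion.** The point holds in a limited form. The stated primary objective is not the aim for which 15 per group was argued, no planned analysis links features to recurrence, and the rank of the reliability aim differs between sections 3.2 and 11. The design therefore cannot support a confirmatory or causal statement about factors for recurrence.

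Under the stated assumptions (two-sided 5%, 80% power, 12-month reading of 70%-90%, yes/no recurrence), only differences of 1.66 to 3.14 SD are detectable, and power at 0.8 SD is 11% to 27%. The absence of a planned analysis and of a matching sample-size rationale does not depend on those assumptions.

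It does not follow that the follow-up is useless. Generating hypotheses remains possible, and very large differences could show. The change should be made, because it alters what the study may conclude, but it does not call the data collection into question.

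**What to change.** Make these changes in one amendment:

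- **Sections 1, 3.1 and 8.3.** Reword the recurrence objective as: *describe candidate movement and muscle-activity features associated with recurrent instability, for testing in a later study*. State that no factor will be reported as identified or responsible on these data.
- **Sections 3 and 11.** Use one order of aims throughout. Either make measurement error (SEM with 95% CI, per group) the primary objective, which matches section 8.1, or keep the reworded recurrence objective as primary and correct the phrase in section 11. Both are defensible, and the choice is the investigators'.
- **Section 8.3.** Add a descriptive comparison of the session features by recorded episodes, with estimates and 95% CIs.
- **Section 8.1.** State the expected precision for both aims: the likely split with its interval widths, and the SEM limits (about 0.86-1.19 times the estimate with 6 repetitions, 0.90-1.12 with 12, assuming independence). Note that a within-session SEM leaves out marker re-placement error.

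The cost is a more modest headline and an amendment, which may need ethics review under section 11 if it is substantial. No extra participants, visits or measurements are needed. An alternative would keep section 3.1 as it stands and add a prespecified analysis of features against recurrence, with a sample size to match. On the same assumptions and a normal approximation, a difference of 0.8 SD would need (2.80/0.8)²/(r(1 − r)) cases, where r is the recurrence proportion: 59 at 70% and 137 at 90%, against the 15 planned.

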#### 3.2 Secondary Objectives

The secondary research objectives used to address the main aim of the study are:

- Validation of a 3D movement analysis protocol for measuring upper limb function in children with shoulder instability.
- Obtain new data on muscle activity and movement patterns of children with and without shoulder instability
- Categorising clinical presentations of instability and identification of important factors for recurrent instability

This is not an experimental study and so there is not a single/primary outcome measure. The following outcomes will be derived from this study

*For the single movement analysis session:*

- **Kinematic** variables related to the movement tasks, for example
  - joint angles (degrees)
  - displacement (position, speed and associated derivatives)
- **Kinetic** variables related to the movement tasks, for example
  - forces/ strength (n, kg/force)
- **Muscle activity patterns** related to the movement tasks, for example
  - Surface electromyography (sEMG) (mv)

*For the follow up outcomes:*

- Number of recurrent episodes of instability

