	
8. Biceps Brachii
 
Location: Electrodes need to be placed on the line between the medial acromion and the fossa cubiti at 1/3 from the fossa cubiti.
 
Orientation: In the direction of the line between the acromion and the fossa cubiti
 
Clinical test: Place one hand under the elbow to cushion it from table pressure and flex the elbow slightly below or at a right angle, with the forearm in supination. Press against the forearm in the direction of extension.
 
With their elbow flexed to 90°
 
Prompts to participants for testing: “Bend your elbow”
 
Guidelines: SENIAM

	
9. Common Flexor Origin
 
Location: About 3-5 centimetres from the elbow joint at distal ventral aspect of forearm. Assessor would ask subject to flex elbow to palpate flexors bulk.
 
Orientation: with the electrodes oriented in the direction of the muscle fibres which run longitudinally down the forearm.
 
Clinical test: Flexion of the wrist
 
Prompts to participants for testing: “Bend your wrist down”
 
Guidelines: Criswell et al 2010

Source: Copyright © Clinical Resources, Inc.

[figure not shown]
[figure not shown]
	
10. Common Extensor Origin
 
Location: About 3-5 centimetres from the elbow joint at proximal dorsal aspect of forearm. Assessor would ask subject to extend elbow and wrist, to palpate extensors bulk. Electrode is placed in the centre of the muscle bulk.
 
Orientation: with the electrodes oriented in the direction of the muscle fibres which run longitudinally down the forearm.
 
Clinical test: Extension of the wrist
 
Prompts to participants for testing: “Bend your wrist up”
 
Guidelines: Criswell et al 2010

--	---

[figure not shown]
[figure not shown]
[figure not shown]
*Source: Copyright © Clinical Resources, Inc.*

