### 8.3 Statistical analysis plan

The aim of this study is to identify factors responsible for recurrent shoulder instability in children. To meet the main aim, the following objectives, need to be met. The methods of analysis used to meet the study objectives have been reported below.

The analysis of measurement units will inform the main study objective and secondary objectives.

- **Kinematic** data such as joint angles and displacements – average range of movement values, as well as absolute minimum and maximum values will be reported for all functional tasks. For comparison purposes, descriptive statistics will be used to report the group behaviours and variability including means and standard deviations.
- **Kinetics** - force/strength – The range of force and strength values, as well as absolute minimum and maximum values will be reported for all functional tasks. For comparison purposes, descriptive statistics will be used to report the group behaviours and variability
- **Muscle activity patterns** - muscle activity (absence or presence), timing of muscle onset, percentage of maximum contraction and time of peak intensity will be used. This methodology is consistent with previously published research and is used for informing clinical decision making processes

The secondary research objectives used to address the main aim of the study are:

1. Validation of a 3D movement analysis protocol for measuring upper limb function in children with shoulder instability.
  - i) Individual variability (associated with of the measurement units outlined above) will be determined using the coefficient of variation for all data.
  - ii) The reliability and error associated with the protocol will be determined using the standard error of measurement for the measurement units outlined above. The reliability of the protocol will be determined through a sensitivity analysis investigating what effect perturbation of the virtual markers has on the outputs of the biomechanical model e.g. kinematics, position of the humerus
2. Obtain new data on muscle activity and movement patterns of children with and without shoulder instability
  - i) The method of analysis outlined above will inform this objective
3. Categorising clinical presentations of instability and identification of important factors for recurrent instability

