  - i) data from study objective 2 will be evaluated to identify features i.e. movement or muscle activity patterns, which may be used to categorise clinical presentations of shoulder instability. An appropriate clustering/categorisation method will be selected once the characteristics of the dataset has been established

if we get a large enough sample size of participants with a homogenous clinical presentation and if three or more groups are identified in the preceding work package, an analysis of variance (ANOVA) can be used. For less than three groups, an independent sample t-test will be used.

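### The plan sets out to find factors among 30 to 210 continuous sEMG features on 15 v 15 children, with no main comparison, no rule for separating a factor from chance, and no provision for finding no distinct groups

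*Combined protocol and SAP*

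**What the plan says.** Section 3.1: "The primary objective of this study is to identify factors responsible for recurrent shoulder instability in children". Section 3.2 then lists kinematic, kinetic and muscle-activity outcomes by example only, and explains the lack of a main one: "This is not an experimental study and so there is not a single/primary outcome measure".

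Section 8.1 gives the size and its basis: "Our rationale for selecting a sample size of 15 in each group (30 total) has been based on previous work". It adds that "A power calculation, used to determine the required sample size, is not possible for this study".

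Section 8.3 makes the comparison of kinematic and kinetic data descriptive. For sEMG it says "muscle activity (absence or presence), timing of muscle onset, percentage of maximum contraction and time of peak intensity will be used". For the third secondary objective, features from the same data are to be used to categorise presentations, by a clustering method selected once the dataset's characteristics are known. Provided the sample is large and homogeneous enough, "if three or more groups are identified in the preceding work package, an analysis of variance (ANOVA) can be used"; otherwise, "For less than three groups, an independent sample t-test will be used".

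The document states no significance level, multiplicity adjustment, criterion for the number of groups, stability check on the groups, or action if no groups appear.

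**The concern.** Being observational is no reason to have no main comparison. A study whose task is to select factors from many candidates needs one more than most, because the largest of many differences is large even when nothing is there. Ranking by size has this problem as much as ranking by p-value, so a descriptive plan is not protected.

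The categorisation step adds a second route. Clusters are formed from features, and the tests that follow may be run on those same features. Groups that were built to differ will then be found to differ. Both branches in 8.3 lead to a comparison between groups, and neither test can be run if there is only one.

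At stake is what the study hands on. Section 1 says identified patterns could inform exercise prescription and referral. With 15 affected children, a chance pattern could look as convincing as a real one.

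**Working it through.** The plan has no power or error figure to reproduce; 8.1 says none was possible. The check is what chance alone produces.

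**Inputs**
- Children: 15 v 15 (8.1).
- Muscles: 10 (7.6.3, the last being "10. Common Extensor Origin").
- Movement tasks: 3 physiological (7.7.2) + 1 functional (7.7.3) + 3 under load (7.7.4) = 7. Grip strength is not counted.
- sEMG measures: 4 (8.3), of which 3 are continuous and 1 is absence/presence.
- Assumptions, because the document is silent: two-sided 0.05 per feature wherever a test is priced; k-means wherever clustering is priced.

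**Number of continuous sEMG features**
- All seven tasks: 10 x 7 x 3 = 210.
- Only the one task headed functional: 10 x 1 x 3 = 30.

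Section 3.2 refers to the movement tasks in general, which favours 210. Section 8.3 restricts kinematic and kinetic reporting to functional tasks and gives no scope for sEMG, so 30 cannot be ruled out. Joint angles, displacements and forces come on top.

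**Largest difference under no effect (no significance level needed)**

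Simulated null data, 3,000 datasets per row, d = difference in means / pooled SD:

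| Features | Correlation within muscle | Median largest \|d\| | 5th-95th percentile |
|---|---|---|---|
| 30 | 0 | 0.87 | 0.64-1.25 |
| 30 | 0.8 | 0.82 | 0.55-1.26 |
| 210 | 0 | 1.17 | 0.95-1.54 |
| 210 | 0.5 | 1.13 | 0.87-1.51 |
| 210 | 0.8 | 1.01 | 0.73-1.42 |

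For scale, the difference that one prespecified feature detects with 80% power at two-sided 0.05 is (1.96 + 0.84) x sqrt(2/15) = 1.02 SD by the normal formula, or 1.06 SD by the noncentral t.

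**If every feature were tested at the assumed 0.05**
- Expected false positives: 30 x 0.05 = 1.5; 210 x 0.05 = 10.5. Correlation does not change the expectation.
- Chance of at least one, independent features: 1 - 0.95^30 = 0.79; 1 - 0.95^210 > 0.999.
- With 210 features and correlation: 0.997 and 0.94 (within-muscle 0.5 and 0.8); 0.99, 0.91 and 0.63 if all features share a common correlation of 0.3, 0.5 and 0.7.

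**Cluster, then test the same features**

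Structureless data, 15 children, 210 features, k-means, 400 runs per setting:

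| Groups | Correlation within muscle | Runs with any p<0.05 | Mean features with p<0.05 |
|---|---|---|---|
| 2 | 0 | 100% | 17.3 |
| 3 | 0 | 100% | 17.9 |
| 2 | 0.5 | 100% | 35.9 |
| 3 | 0.5 | 100% | 38.2 |

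With 210 tests, some p<0.05 would be expected anyway. The sign of circularity is the count: 17 to 38 features, against 10.5 for labels unrelated to the data.

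**The case against.** The best defence is that the plan is modest. The case-control comparison is descriptive, so a programme of 210 tests at 0.05 is not what 8.3 describes. ANOVA and the t-test appear only after categorisation, conditionally. Section 2 presents the project as a step towards biomechanical models, and 8.1 says the data will inform future power calculations.

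Much of this stands, and it limits four stronger readings that a reader might infer:
- *That the plan bars a no-groups result.* It does not. It is silent, and its wording on features and groups is tentative.
- *That 210 is a minimum.* It depends on all seven tasks being analysed for sEMG; 30 is the low reading.
- *That about ten false positives will be reported.* That is an expectation under an assumed level and an assumed testing programme. Under strong common correlation, a dataset may contain none.
- *That noise will certainly be split into convincing categories.* No clustering method is named. K-means with a silhouette choice over two to five groups returned three or more groups in roughly 43-73% of noise datasets. It cannot return one group, but that is a property of the assumed algorithm. The median best silhouette was only 0.36, 0.16 and 0.06 with 3, 10 and 50 features, so a careful reader of that index would often see weak or no structure.

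The core remains. The largest-difference result needs no significance level and applies to a purely descriptive comparison. The condition on sample size carries no number and does not govern the clustering. Nothing in the document labels the factors as hypothesis-generating.

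**Conclusion.** The concern holds in this form. A factor-finding objective is paired with no main comparison and no rule for separating a factor from chance. On sEMG features alone, the largest purely chance difference is typically 0.8-0.9 SD (30 features) to 1.0-1.2 SD (210). At the upper end, that matches the 1.06 SD that the study could reliably detect for one feature chosen in advance. Clustering by a method chosen after seeing the data, then testing clusters on the features that formed them, gives significant results from noise essentially always under k-means.

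The count rests on which tasks are analysed, the false-positive figures on an assumed two-sided 0.05, and the clustering figures on k-means. The largest-difference figures rest only on the feature count, group size and the correlations shown, with normal data. The plan should be changed; the data collection need not be.

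**What to change.** Amend 3.2 and 8.3 before any data are examined.

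1. **Main comparisons.** Name up to five features, tied to the mechanisms in section 2, as the main case-control comparisons. Report simultaneous 95% confidence intervals (for example Holm or Bonferroni). Five unadjusted intervals would leave up to 1 - 0.95^5 = 23% chance of at least one wrongly excluding zero if independent.
2. **All other features.** Label them hypothesis-generating. Call one a candidate factor only if it survives a max-T permutation or Benjamini-Hochberg adjustment. Permute labels over children, not repetitions, and within matched pairs or age strata if the matching is individual. Describe survivors as associated with instability. Report their relation to 12-month recurrence among cases separately, since a case-control difference does not itself address recurrence.
3. **Categories.** Cluster on the named features only, test against a single-group null (gap statistic or permutation), and report that there are no distinct categories if it is not rejected. Do not test clusters on the features used to form them.

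The cost is SAP wording and a short permutation script, with no extra children, visits or measurements. The downside is real: fewer features will be declared. With Bonferroni over five, the difference detectable with 80% power rises from 1.02 to (2.58 + 0.84) x sqrt(2/15) = 1.25 SD by the normal formula (1.33 SD by noncentral t). For the non-named features it is about 1.9 SD under Bonferroni over 210, so power there is low and the short list has to be chosen with care.
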